10.5 Serious adverse events

10.5.1 Definition of a serious adverse event

A serious adverse event is any untoward medical occurrence that results in death, is life threatening, results in persistent or significant disability/incapacity, requires in-patient hospitalization or prolongation of existing hospitalization or is a congenital anomaly/birth defect in the offspring of a study subject. In addition, important medical events that may jeopardize the

Page 55 of 96 Version 17, DEAP/MRTC/MMVDU CONFIDENTIAL

patient or may require intervention to prevent one of the other outcomes listed above will be considered serious.

- Life threatening—definition: An adverse event is life threatening if the participant was at risk of death at the time of the event; it does not refer to an event, which hypothetically might have caused death, if it were more severe.
- Disabling/incapacitating—definition: An adverse event is incapacitating or disabling if the event results in a substantial disruption of the participant's ability to carry out normal life functions. This definition is not intended to include experiences of relatively minor medical significance such as headache, nausea, vomiting, diarrhea, influenza, and accidental trauma (e.g. sprained ankle).
- Hospitalization: In general, hospitalization signifies that the participant has been detained (usually involving at least an overnight stay) at the hospital or emergency ward for treatment that would not have been appropriate in the physician's office or outpatient setting.

10.5.2 Reporting serious adverse events

In the event that one or more serious adverse reactions probably or suspected of being related to vaccination are detected following any immunization in any of the vaccine groups, no further vaccinations will be administered until a written report has been submitted to DMID, U.S. Army HSRRB, University of Maryland IRB, and the FMPOS Ethics Review Committee and the investigators have conferred with the Local Medical Monitor and SMC.

Any serious adverse events occurring during the study period whether or not considered to be related to the study vaccine/comparator will be reported within 24 hours of the PI being notified to the IND sponsor (USAMMDA) by telephone, followed by faxing of the complete AE reporting form to the Sponsor. SAEs will also be reported within 24 hours by telephone or E-mail to the Local Medical Monitor, SMC and the FMPOS Ethics Review Committee in Mali. Any death or SAE that is related to the study vaccine will be reported to DMID and GSK-Biologicals within 24 hours of the PI being notified. A written report will follow the initial report within 3 working days. The report will be sent to the Quality Assurance Office, USAMMDA (cf. Appendix 17.2)

Notifications and reports will be provided by USAMMDA to the following agencies by Internet, e-mail, fax or telephone within the reporting deadlines required by each agency: the cosponsor (DMID), the University of Maryland School of Medicine IRB, the Food and Drug Administration, and the HSRRB. All SAE reports and follow-up information will be reported to GSK-Biologicals by fax, phone, or E-mail within 24 hours of the PI becoming aware of the SAE. The rationale for USAMMDA serving as the primary contact point for disseminating all SAE reports to these bodies (with the exception of GSK Biologicals) is that communications at the field site are limited, and while every effort will be made to build redundancy into the communications systems, it is possible that phone land lines and E-mail could be down simultaneously, leaving only satellite phones as a means of communication from Bandiagara. The PI and co-PI on site will make every effort to directly notify all IRBs, sponsors and partners directly within their required reporting deadlines, in addition to the notifications they will receive from USAMMDA.

Every serious adverse event that is not resolved at the time the initial written report is filed will have a follow-up report submitted when information is available. Any submitted report will be identified as "initial", "follow-up", or "medical monitor". The initial notification will include:

Page 56 of 96 Version 17, DEAP/MRTC/MMVDU CONFIDENTIAL

- The study protocol number and the name of the PI
- The participant study number, sex and age
- The date of onset of the SAE, and date of administration of study vaccine(s)

The PI will not wait to collect additional information to fully document the event before making notification of a serious adverse event. The telephone/e-mail report will be followed by a full written report using the SAE form within the CRF, detailing relevant aspects of the adverse events in question.

Instances of death, cancer or congenital abnormality in offspring of a study participant if brought to the attention of the investigator AT ANY TIME after cessation of the study AND suspected by the Investigators to be related to study medication will be reported to the sponsors and GSK Biologicals within four weeks of coming to the knowledge of the PI.

10.6 Pregnancy

Participants who become pregnant during the study period (up to 30 days after receiving the last study immunization) will not receive additional study immunizations but may continue other study procedures.

Female participants will be instructed to notify the investigators if they become pregnant at any time during the 12-month study period. Although not considered an adverse event pregnancy will be reported in the same way as an adverse event. All pregnancies occurring during the study period will be followed to term (with permission of the participant), any premature termination reported, and the health status of the mother and child including date of delivery and the child's gender and weight will be reported to HSRRB with copy to DMID and GSKBio.

10.7 Treatment of adverse events

The investigators will provide treatment of adverse events . Advice will be sought from the Local Medical Monitor and other medical specialists as indicated for severe, unusual or complicated medical conditions. Treatment events will be fully documented.

11 PARTICIPANT COMPLETION AND DROP-OUT

11.1 Definition

From the perspective of data analysis a 'drop-out' is any participant who did not come back for the concluding visit foreseen in the protocol. A participant who returns for the concluding visit foreseen in the protocol is considered to have completed the study.

11.2 Procedure for handling drop-outs

Investigators will attempt to contact those participants who missed scheduled surveillance visits. Information gathered will be described on the Study conclusion page of the CRF and on Medication/Adverse event forms as appropriate.

Page 57 of 96 Version 17, DEAP/MRTC/MMVDU CONFIDENTIAL

11.3 Reasons for drop-out

The Study conclusion page on the CRF will specify which of the following possible reasons were responsible for dropout of the participant from the study:

- Serious adverse event
- Non-serious adverse event
- Protocol violation (to be specified)
- Withdrawal of study consent, not due to an adverse event
- Migration from the study area
- Lost to follow-up
- Other (to be specified)

12 DATA MANAGEMENT AND ANALYSIS

Data entry will be performed on site and in the MRTC/MMVDU data management unit in Bamako if necessary. The MRTC data management unit will do data analysis and reporting for primary and secondary endpoints in collaboration with the CVD statistician.

12.1 Primary endpoints

Occurrence of solicited symptoms during a 7-day surveillance period after vaccination (day of vaccination and study days 1, 2, 3 and 7).

Occurrence of unsolicited symptoms during a 30-day surveillance period after vaccination.

Occurrence of serious adverse events during the study period.

12.2 Secondary endpoints

Anti-AMA1 antibody titers at time points at which blood samples are collected for serology.

Inhibition of parasite growth by the in vitro GIA to 3D7.

Specificity of the antibodies to diverse AMA1 genotypes in addition to 3D7, by measuring by ELISA, and GIA on parasites with typed AMA1.

12.3 Study cohorts/datasets to be evaluated

Total cohort

The 'Total Cohort' will include all participants enrolled (defined as randomized to study groups) in the study.

Safety cohort

The 'Safety Cohort' will consist of all participants who have received at least one dose of study vaccine or comparator and for whom any data on safety are available.

Page 58 of 96 Version 17, DEAP/MRTC/MMVDU CONFIDENTIAL

The presentation of safety data will explore separately the adverse experiences among participants who received all vaccinations, among those who received only some and among those with clinical violations of study protocol.

Immunogenicity cohort

The 'Immunogenicity Cohort' will include all evaluable participants (i.e., those meeting all eligibility criteria, and who have received at least one immunization with any of the study or control vaccines) for whom data concerning immunogenicity endpoint measures are available. This will include participants for whom assay results are available for antibodies against at least one study vaccine antigen component after vaccination.

12.4 Estimated sample size

This Phase 1 trial is not powered to detect differences between groups. Even if comparative statistics for the safety variables are computed, the study will have low power to detect anything other than very large differences in the incidence of local and general side effects between the vaccination groups. This is done weighing the need to detect any possible untoward reactions against the need to limit the number of volunteers involved for safety purposes. The sample size of 20 in each study group is widely accepted and used in industry for the initial assessment of the safety, tolerance and immunogenicity of an investigational vaccine. Incorporation of a comparator vaccine as control will enable broad initial estimates of the incidence of local and general side effects and of immune responses among vaccine recipients.

Page 59 of 96 Version 17, DEAP/MRTC/MMVDU CONFIDENTIAL

Event Rate	Pr 0/20	Pr 1+/20
0.01	0.82	0.18
0.05	0.36	0.64
0.08	0.19	0.81
0.10	0.12	0.88

Table 6. Event detection probability table.

Event rate. True rate at which an event occurs.

Pr 0/20. Given the event rate, probability that no events will be detected among 20 vaccinees.

Pr 1+/20. Given the event rate, probability that one or more events will be detected among 20 vaccinees.

If the SAE rate is 8%, then the probability of observing at least one event in a group size of 20 (Pr 1+/20) is 0.81. If the SAE rate is 8%, then the probability of observing no event in a group size of 20 (Pr 0/20) is 0.19.

12.5 Primary analysis

A final research analysis plan will be agreed upon by the investigators, DMID, WRAIR and GSKBio prior to locking of the database for the final analysis. This plan will include information on adverse events by dose and number of vaccinations. The primary analysis will be conducted on data collected until Day 90 (30 days post Immunization 3). The data generated at this time will be used for decision-making related to the product clinical development plan. The study will continue in a single blind manner for additional safety surveillance and immunogenicity assessment. This additional information will be appended to the study report. It is anticipated that the results of this study will be presented to the scientific community via oral presentations at meetings and written publications in scientific journals. The data to be presented and the authorship will be discussed between investigators and sponsors, and approved by the sponsors, prior to any official communication.

The official report of the primary analysis will be submitted through appropriate channels and upon approval by the WRAIR, Dept. of Immunology to the Human Use Review and Regulatory Affairs Division at Ft. Detrick, MD. This report will contain detailed information about the participants, their tolerance of the vaccines, their side effects and laboratory abnormalities, as well as their overall immune responses to immunization.

12.5.1 Analysis of demographics

Demographic characteristics (age, sex and place of residence) of each study cohort will be tabulated. The mean age (plus range and standard deviation) by sex of the enrolled participants, as a whole and per group will be tabulated.

12.5.2 Analysis of immunogenicity

Immunogenicity will be assessed in several ways. A series of graphs will display immunologic responses. For each vaccine group and time point, the distribution of anti-AMA1 antibody levels and reverse cumulative distribution curves will be plotted. Corresponding summary statistics will show means and standard deviations as well as median, 25th and 75th

Page 60 of 96 Version 17, DEAP/MRTC/MMVDU CONFIDENTIAL

percentiles, and 10th and 90th percentiles. The results will be presented both as raw data and as log-transformed data.

In addition, for each treatment group and time point, anti-AMA1 antibody levels will be presented as geometric means of OD units with 95% confidence intervals. For each vaccine group and for each time point, a table will show the proportion of volunteers with two-fold, four-fold, and eight-fold increases in anti-AMA1 antibody titers.

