3 SUMMARY

Title Indication/ Study Population	Double blind randomized, controlled Phase I dose escalation trial to evaluate the safety and immunogenicity of the WRAIR AMA1 malaria antigen (FMP2.1) adjuvanted in GSK's AS02A vs. rabies vaccine in malaria-experienced adults in Bandiagara, Mali HEALTHY MALARIA-EXPERIENCED ADULTS AGED 18-55 YEARS				
Principal Investigator	[name]., M.P.H.				
Rationale	In a small clinical study in malaria-naïve adults FMP2.1/AS02A was acceptably safe and immunogenic. This will be the first study in an endemic area and will evaluate the safety and reactogenicity of $25\mu g$ and $50\mu g$ dose levels of FMP2.1/AS02A in malaria-experienced adults.				
Objectives	Primary				
	To evaluate the safety and reactogenicity of 25µg and 50µg of WRAIR's AMA1 malaria antigen (FMP2.1) adjuvanted in GlaxoSmithKline Biologicals' AS02A compared to rabies vaccine in malaria-experienced Malian adults.				
	Secondary				
	To evaluate the humoral and cellular immune responses and growth inhibition responses to 25µg and 50µg of WRAIR's AMA1 malaria antigen (FMP2.1) adjuvanted in GlaxoSmithKline Biologicals' AS02A compared to rabies vaccine in malaria-experienced Malian adults.				
Study design	 Double blind, randomized, controlled (RabAvert® Rabies vaccine) Phase 1 dose escalation Three study groups: 25µg FMP2.1, 50µg FMP2.1, and rabies vaccine One study center Study duration: approximately 12 months per subject Immunization schedule: Study days 0, 30 and 60 Route: IM in deltoid muscle 				
Number of subjects	• 60 subjects				
Convincer of Subjects	• Occurrence of solicited symptoms after each vaccination during a 7-				
Co-primary endpoints	day surveillance period (day of vaccination and study days 1, 2, 3 and				
Secondary endpoints	 Occurrence of unsolicited symptoms after each vaccination during a 30-day surveillance period. Occurrence of serious adverse events throughout the study period. Titers of anti-AMA1 antibody at each time point where serology samples are analyzed. Cellular immune responses to FMP2.1 at baseline and after immunization 				
	Parasite growth inhibition by the in vitro GIA				

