Preliminary studies in Donéguébougou, Mali, demonstrate that natural antibodies exist in a large proportion of individuals (>90%) in this area of intense, seasonal, transmission. In a cross-sectional study of 200 individuals aged 6 months to 45 years conducted in 2002 and 2003, median anti-AMA1 antibody titers reached approximately 1000 at the peak of malaria transmission, although significant variation was seen between different age groups (45).

The naturally acquired antibodies to AMA1 found in people living in malaria-endemic areas have also been shown to inhibit in vitro the growth of *P. falciparum* (46). In this study, human anti-AMA1 IgG was affinity purified from a pool of plasma obtained from Papua New Guinean blood donors who had previously been found to have high titers of antibodies to a variety of *P. falciparum* asexual blood-stage antigens. The affinity-purified human anti-AMA1 antibodies inhibited various strains of *P. falciparum* in a manner similar to that observed with rabbit IgG raised to refolded *P. falciparum* AMA1 3D7, in the *in vitro* merozoite invasion assay. This inhibition was dose-dependent and anti-AMA1 antibodies recognized both strain-specific and conserved epitopes. From this evidence, it is reasonable to postulate that boosting the natural antibody response to AMA1 through vaccination may protect an individual from illness due to the asexual blood stage of *P. falciparum* infection.

The study proposed here is a Phase 1 safety and immunogenicity study of an AMA1derived vaccine in Malian adults, in an area of seasonal and intense malaria transmission. This will be the first study of the FMP2.1/AS02A candidate vaccine in a malaria-experienced population. If shown to be safe and immunogenic, further studies will be planned with this formulation to assess its safety and efficacy in children, either alone or in combination with other malaria vaccine candidates, possibly including RTS,S, other genotypes of AMA1, or other blood stage antigens such as the MSP1-based vaccine currently being tested in Mali.

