4.3.10 Comparator Vaccine

4.3.10.1 Rationale for rabies comparator vaccine

Having a comparator vaccine is particularly useful in Phase 1 trials conducted in malariaendemic areas, since background immunity and natural exposure to malaria may make it difficult to interpret immunogenicity data. This is particularly a concern in this trial in a setting with seasonal malaria when transmission intensity will be increasing during the period when vaccine is being administered. Rising titers of antibody to AMA1 could be due to immunization or to natural exposure or both. The use of a control group will permit comparison of immune responses and will result in a clearer interpretation of serological results. While a placebo control group would accomplish this same end, using a vaccine that is beneficial to the subjects increases

Page 27 of 96 Version 17, DEAP/MRTC/MMVDU CONFIDENTIAL

the benefit to risk ratio, which is always relatively low in a Phase 1 trial. We have chosen to use rabies vaccine as the comparator for several reasons: 1) the dosing schedule is compatible with that of FMP2.1; 2) to be able to compare results directly with recent and ongoing studies of the FMP1/AS02A vaccine in Mali and Kenya that used rabies vaccine as a comparator; and 3) the available evidence supports a benefit for participants who receive rabies vaccine.

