12.5.3 Analysis of safety

The overall percentage of participants with at least one local adverse event (solicited or unsolicited) and the percentage with at least one general adverse event (solicited and unsolicited) during the 7-day surveillance period after vaccination will be tabulated. The incidence, intensity and relationship of individual solicited symptoms over the 7-day surveillance period will be calculated per group and vaccine administration.

The number of participants with at least one report of an unsolicited adverse event, classified by WHO-preferred terms, reported up to 29 days after vaccination will be tabulated per group and vaccine administration. The intensity and relationship to vaccination of the unsolicited symptoms reported will also be assessed.

Serious adverse events are expected to be rare, but where observed will be described. Comparisons between study groups of incidence of symptoms, local and general symptoms will be made based on a two-sided Fisher's Exact Tests. Analysis of safety during the 12-month surveillance period will consist of comparison of incidence of serious adverse events as well as hemoglobin, creatinine and ALT levels.

Clinical laboratory parameters

Hematological (CBC) and biochemical (ALT, creatinine) laboratory parameters will be measured at specific time points, Days 0, 7, 14, 30, 37, 44, 60, 67, 74, 90 and starting on day 180 every 3 months. Clinically relevant abnormal values will be tabulated and a trend analysis could be performed if deemed necessary.

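### Section 12.5.2 pre-specifies no vaccine-versus-rabies immunogenicity estimate and does not use the Day 0 titre as a covariate

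*Combined protocol and SAP*

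**What the plan says.** The Summary's secondary objective opens "To evaluate the humoral and cellular immune responses and growth inhibition responses to" the two doses, and it names rabies vaccine as the comparator. Section 4.3.10.1 explains why this matters at the site: transmission will be rising while vaccine is given, and "Rising titers of antibody to AMA1 could be due to immunization or to natural exposure or both". It then says: "The use of a control group will permit comparison of immune responses and will result in a clearer interpretation of serological results".

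Section 12.5.2 sets out the antibody analysis, all of it by group and time point:

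- a fold-rise table: "For each vaccine group and for each time point, a table will show the proportion of volunteers with two-fold, four-fold, and eight-fold increases". The reference time point for the increase is not stated;
- plots: "the distribution of anti-AMA1 antibody levels and reverse cumulative distribution curves will be plotted";
- means, standard deviations, medians and outer percentiles, on the raw and log scales;
- interval estimates within each group: "for each treatment group and time point, anti-AMA1 antibody levels will be presented as geometric means of OD units with 95% confidence intervals".

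The only between-group procedure named in section 12.5 concerns symptoms. In section 12.5.3, comparisons "will be made based on a two-sided Fisher's Exact Tests". Section 4.3.12 pools the two sets of ten rabies recipients into one group. Section 8.1 schedules serum for antibody at Day 0 and at Days 14, 30, 44, 60, 74 and 90.

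**The concern.** The protocol identifies natural boosting as a rival explanation for rising titres and includes a control group partly to deal with it. The analysis section then stops one step short: it summarises vaccine and rabies recipients side by side and never states the quantity that compares them. Whoever reads the Day 90 report must form that comparison informally, and section 12.5 says those data will feed decisions on clinical development.

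Baseline matters because titres in exposed adults need not start low or alike. Section 4.3.1 reports that at another Malian site more than 90% of people had natural antibody, that "median anti-AMA1 antibody titers reached approximately 1000 at the peak of malaria transmission", and that levels varied between age groups. With 20 per group, a chance imbalance at Day 0 can carry into the post-dose means. The Day 0 sample could remove much of that, but it is not used as a covariate.

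**Working it through.** **1. The plan's own figure.** Table 6 is the only sample-size calculation. With 1 − (1 − p)^20, event rates of 0.01, 0.05, 0.08 and 0.10 give 0.182, 0.642, 0.811 and 0.878, matching the stated 0.18, 0.64, 0.81 and 0.88. It concerns event detection. No corresponding immunogenicity figure is given.

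**2. What the planned displays already allow.** Write V for a vaccine group and R for pooled rabies, each n = 20, with log-scale mean m and SD s. The unadjusted log ratio is m_V − m_R, with standard error √(s_V²/20 + s_R²/20). Every term is in the planned summaries, so a reader could work out an unadjusted ratio and interval.

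**3. What they do not allow.** The baseline-adjusted log ratio is (m_V − m_R) − b(x_V − x_R), where x is the mean log Day 0 titre and b the within-group slope of post-dose on Day 0 titre. Per-group means, SDs and percentiles do not give b, so this estimate has to be planned.

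**4. Precision gain.** With correlation r between log Day 0 and log Day 90 titre, and similar slopes in the groups, the variance of the contrast is multiplied by 1 − r²:

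- r = 0.2: 1 − 0.04 = 0.96, a 4% reduction;
- r = 0.5: 1 − 0.25 = 0.75, a 25% reduction;
- r = 0.7: 1 − 0.49 = 0.51, a 49% reduction.

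**5. Illustration for a true 2-fold ratio.** The documents give neither the SD of log10 titre nor r, so both are assumed. Power = Φ(log10 2 / [SD·√(1 − r²)·√(2/20)] − 1.96). The last column is the simulated chance (40,000 runs) that two separate per-group 95% intervals fail to overlap.

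| SD (log10) | Unadjusted | r = 0.2 | r = 0.5 | r = 0.7 | Intervals do not overlap |
|---|---|---|---|---|---|
| 0.3 | 0.89 | 0.90 | 0.96 | 0.99 | 0.59 |
| 0.5 | 0.48 | 0.49 | 0.59 | 0.76 | 0.17 |
| 0.7 | 0.27 | 0.28 | 0.35 | 0.48 | 0.07 |

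For a true 8-fold ratio the non-overlap chance is 1.00, 0.996 and 0.87 at the three SDs. A large effect is visible in the planned displays; a 2-fold one often is not.

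As interval width, the 95% limits are the estimated ratio divided and multiplied by 10^(1.96·SD·√(1 − r²)·√0.10). At SD 0.5 that factor is 2.04 unadjusted, 2.01 at r = 0.2, 1.86 at r = 0.5 and 1.66 at r = 0.7.

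**6. Effect of a cohort term.** Each dose is given in one cohort only (section 7.1.2). With cohort in the model, each dose is compared only with the ten rabies recipients of its own cohort. The variance multiplier changes from 1/20 + 1/20 = 0.10 to 1/20 + 1/10 = 0.15, a factor of 1.5 before baseline adjustment. At SD 0.5 the unadjusted interval factor rises from 2.04 to 10^(1.96·0.5·√0.15) = 2.40.

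**The case against.** The case for leaving the section alone has weight. Immunogenicity is secondary, section 12.4 says the trial is not powered for group differences, and the objectives in section 5.2 are worded as measurement rather than comparison. Section 12.5 defers a final analysis plan to before database lock. That plan is not among the documents, so it may contain such a contrast.

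Much of this stands, and it limits the point. Several stronger readings are tempting but unsupported:

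- A reader might infer that the trial cannot separate vaccine response from natural boosting. It can, descriptively. Rabies is summarised at every time point, the fold-rise table shows change within participants, and the planned log-scale means and SDs yield an unadjusted ratio.
- A reader might infer that groups will be judged by overlap of intervals. No section says so; the non-overlap column only shows what informal reading could miss.
- A reader might infer that participants with high starting titres seldom reach a 4-fold rise. The documents give no data on this. The figure of over 90% with natural antibody comes from a different site and an age range from 6 months to 45 years.

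The objection does not remove the gap. An estimate with an interval needs no claim of power, and section 12.5.3 plans between-group tests for symptoms despite the same disclaimer. The only content section 12.5 names for the later plan is adverse events by dose and number of vaccinations.

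**Conclusion.** The point holds in a limited form. No between-group immunogenicity estimate is pre-specified and Day 0 titre is not used as a covariate, so the comparison with rabies rests on informal reading of per-group summaries. The consequence is lost precision and no stated interval for modest effects; large effects would not be missed.

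The size is uncertain. The variance reduction is r², anywhere from slight (4% at r = 0.2) to about half (49% at r = 0.7). It rests on an unknown correlation and on similar slopes across groups; if vaccination flattens the slope, the simple formula no longer applies exactly. The power figures also rest on assumed SDs of 0.3 to 0.7 log10 and a normal approximation.

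A reader might also infer that the rabies group has to be split by cohort in the main analysis. The documents do not require this: section 4.3.12 pools the group. The case for a cohort-adjusted check is that the second cohort enrols after the first, and each 50 µg immunization follows the corresponding 25 µg one by at least 14 days (section 6.1), in a season of rising transmission. Baseline adjustment would repay the 1.5-fold variance only if 1.5(1 − r²) ≤ 1, that is r of at least 0.58, which nothing in the documents establishes.

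**What to change.** Add to section 12.5.2, or to the final analysis plan before database lock:

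1. **Main estimate, Day 90.** A linear model of log anti-AMA1 titre on vaccine group and log Day 0 titre. Report the baseline-adjusted geometric mean ratio of each dose to the pooled rabies group (n = 20) with its 95% CI. Give the same ratios descriptively at Days 14, 30, 44, 60 and 74.
2. **Sensitivity analysis.** Repeat with a cohort term, stating that each contrast then becomes 20 v 10, with about 1.5 times the variance before baseline adjustment.
3. **Fold-rise tables.** Keep them as description, name Day 0 as the reference, and show the difference in proportions from rabies.

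Extending the Day 0-adjusted contrast to GIA and cell-mediated responses is optional. No extra participants, visits or samples are needed; the cost is plan wording and a small amount of analysis.
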